### **1.3. Data from Ongoing Phase I Part of the Study**

A total of 12 patients have been dosed in the ongoing Phase I part of the study since June 2017 with doses of AK01 of up to 75 mg BID. Dose- limiting- toxicities (DLTs) were noted at both 75 mg and 50 mg dose levels. The 25 mg twice a day (BID) dose has been chosen as the dose for Phase II.

Based on safety analysis of the ongoing Phase I part of the study, the following are considered as potential adverse events (AEs): bone marrow toxicity including neutropenia and thrombocytopenia; gastrointestinal toxicity including mucositis and diarrhea; and corneal deposition with blurry vision and double vision. Appropriate follow up and rapid therapy for any of these events will be undertaken.

Additional information on the reported AEs is available in the investigator's brochure (IB).

## **2. STUDY OBJECTIVES**

### **2.1. Phase I**

The primary objective is:

- To determine the maximum tolerated dose (MTD) of AK-01 as monotherapy in patients with locally advanced or metastatic solid tumors.

The secondary objective is:

- To evaluate the tolerability and overall safety profile of AK-01.

The exploratory objectives are:

- To evaluate the pharmacokinetic (PK) and pharmacodynamic (PD) characteristics of AK-01.
- To compare PD markers of AK-01 target engagement in tumor biopsies.
- To assess preliminary evidence of AK-01 anti-tumor activity.

### **2.2. Phase II**

The primary objective is:

- To evaluate the objective response rate (ORR) of AK-01 in up to 4 cohorts of locally advanced or metastatic solid tumor types of interest.

The secondary objectives are:

- To evaluate the tolerability and overall safety profile of AK-01.
- To evaluate the PK and PD characteristics of AK-01.

The exploratory objectives are:

- To evaluate the effect of AK-01 on other clinical endpoints in these indications.
- To evaluate the efficacy of AK-01 in patients with locally advanced or metastatic solid tumor types of interest with different molecular profiles.

### 3. INVESTIGATIONAL PLAN

[figure not shown]
This open-label, non-randomized, multi-center study will explore the safety, PK, PD, and efficacy of AK-01 administered in 21-day cycles to patients with locally advanced or metastatic solid tumors.

In Phase I of this study, patients with locally advanced or metastatic solid tumors (all-comers) will be administered AK-01 according to a multiple ascending dose (MAD) schedule to determine the MTD. The phase II dose (P2D) may be confirmed in up to 6 additional patients, and may take into consideration the MTD, evidence of AurA and AurB target engagement, and PK. The P2D will not exceed the MTD. Throughout Phase I, safety, tolerability, PK, PD, and early evidence of anti-tumor activity will be assessed.

In Phase II of this study, AK-01 will be administered in up to 4 cohorts; initially in patients with SCLC and BC, and subsequently, at the sponsor's discretion, in patients with one of the following: TNBC, HPV associated SCC-HN, and/or any OT that warrants further exploration. Efficacy, safety, PK, and PD will be assessed.

An overview of the study design is given in [Figure 1](#).

**Figure 1. Overview of Study Design**

Notes: Dose escalation in Phase I will follow a 3 + 3 design; dosing may vary from proposed doses for safety reasons. Following identification of the MTD, the P2D may be explored in up to 2 additional cohorts. Phase II will consist of up to 4 cohorts of patients with locally advanced or metastatic 1) BC; 2) SCLC; 3) TNBC; 4) HPV associated SCC-HN; and/or 5) OT that warrants further exploration.

Abbreviations: BC – breast cancer; BID – twice daily; HPV – human papilloma virus; MTD – Maximum Tolerated Dose; OT – other tumor type; P2D – phase II dose; SCC-HN – squamous cell cancers of the head neck; SCLC – small-cell lung cancer; TNBC – triple negative breast cancer

### 3.1. Overall Study Design and Plan – Phase I

In Phase I, approximately 30 patients with locally advanced or metastatic tumors for whom no treatment of higher priority exists will be enrolled. The 3 + 3 method will be used for increasing, maintaining, or decreasing the dose of AK-01.

The following rules and definitions will guide dose escalation.

#### 3.1.1. Dose-Limiting Toxicity

A DLT is any AE during Cycle 1 which is considered by the investigator(s) to be related (possibly or probably) to the IMP, and fulfills at least one of the following criteria using version 4.03 of the National Cancer Institute's Common Terminology Criteria for Adverse Events (NCI CTCAE, see [Appendix 9](#)):

- $\geq$ Grade 3 non-hematological toxicity, except for alopecia. Nausea, vomiting, and diarrhea will NOT be considered DLT unless they have been fully medically managed by institutional guidelines and yet remain  $\geq$ Grade 3 for  $>3$  days.
- Febrile neutropenia of any grade.
- Grade 3 neutropenia or thrombocytopenia lasting  $>5$  days.
- Grade 4 neutropenia or thrombocytopenia.
- $\geq 5$  times upper limits of normal (ULN) aspartate aminotransferase (AST) or alanine aminotransferase (ALT) with  $>2$  times ULN bilirubin. If the liver has tumor involvement, AST and ALT  $\geq 7$  times ULN with  $>2$  times ULN bilirubin will be considered a DLT. In addition, any patient with this degree of hepatic effect will be withdrawn from the study.
- $\geq$ Grade 4 prolongation of QT interval corrected using the Fridericia formula (QTcF, see [Appendix 7](#)) on 2 separate ECG readings approximately 5 min apart.

Patients who exhibit a DLT will require interruption of IMP, and may be discontinued from further participation in the study. Dose modifications for toxicity are described in [Section 3.3.2](#). Patients experiencing a DLT will be medically managed by the investigator in consultation with the sponsor.

See [Section 5.3.2](#) for guidelines on patient replacement.

DLTs will be evaluated for each cohort from the time of first administration of AK-01 through the first 21-day cycle. The frequency of DLTs in the previous cohort will determine whether the dose of the subsequent cohort will increase, decrease, be maintained, or stop.

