### 3.1.4. Inpatient Dose Adjustments

Dose modifications for toxicity are described in [Section 3.3.2](#).

Following Cycle 1, if no DLT-equivalent toxicity is experienced, a given patient’s dose may be maintained or escalated (provided the dose does not exceed the MTD). The decision to dose escalate a patient after Cycle 1 will be recommended by the investigator and discussed with the sponsor’s medical representative. A patient can only be escalated to a dose level at which a

minimum of 3 patients have completed Cycle 1 and which has been deemed acceptable by the SAC. Inpatient AK-01 dose escalation may occur following completion of the patient's current cycle.

Any patient who continues in the study following Cycle 1 will be assessed for toxicity and tolerability throughout their participation. The safety and tolerability of dose escalation in these patients may guide dose decisions for new cohorts.

Following completion of Cycle 1, dosing may continue in 21-day cycles until disease progression if the patient is receiving benefit and is experiencing no severe toxicity in the opinion of the investigator.

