### 3.2. Overall Study Design and Plan – Phase II

Phase II will evaluate the preliminary efficacy of AK-01 in up to 4 cohorts; initially in patients with locally advanced or metastatic SCLC and BC, and subsequently, at sponsor's discretion, in patients with TNBC, SCC-HN, and OT. Up to 30 patients may be enrolled in each cohort, giving an estimated total of up to 120 patients. Since AK-01 is an experimental treatment, patients will need to have failed standard of care therapies (i.e., platinum-based therapy for SCLC; hormone therapy and a CDK4/6 inhibitor for BC; relapsed/resistant TNBC patients; standard therapy for HPV associated SCC-HN) before being enrolled in this trial.

All open cohorts in Phase II may begin enrollment concurrently and will be dosed at 25 mg BID. Dose increases will not be allowed in Phase II. Dose modifications for toxicity are described in [Section 3.3.2](#).

After Cycle 1, dosing of AK-01 may continue in 21-day cycles until disease progression if the patient is receiving benefit, and is experiencing no severe toxicity in the opinion of the investigator.

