### 3.3.2. Dose Modifications for Toxicity

Dose modifications are permitted as described below for toxicities that emerge throughout the study.

IMP may be withheld for up to 21 days to allow sufficient time for recovery from toxicity, but patients who do not recover within this period will be withdrawn. Following recovery, IMP may be resumed at the same dose or at a reduced dosing frequency, depending on the type and severity of toxicity experienced (see [Table 1](#)).

[Table 1](#) describes AK-01 dose modifications for patients who experience toxicity.

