**Table 1. AK-01 Dose Modifications for Toxicity**

Toxicity	Dose Modification
QTcF Prolongation	
<Grade 2	Continue at current dose level.
Grade 2 (QTcF average of triplicate readings >480 msec)	Reduce dosing frequency without interruption. If the event recurs, the dose may be withheld. If the event recurs a third time, dosing may only continue with sponsor approval.

Grade 3 (QTcF average of triplicate readings >500 msec)	Withhold AK-01 for up to 14 days. If QTcF returns to within 30 msec of baseline or <450 msec within 14 days, treatment may be resumed at a reduced dosing frequency. If the event recurs a second time, the dose may again be withheld and resumed after 14 days providing the above criteria are met after 14 days. If a third occurrence is documented, treatment must be terminated.
Grade 4 (QTcF average of triplicate readings >500 msec or >60 msec change from baseline, and TdP or polymorphic ventricular tachycardia or signs/symptoms of serious arrhythmia)	Treatment should be terminated.
Other Non-Hematologic Toxicity	
Grade ≤2	Continue at current dose level.
Grade 3 (except alopecia, nausea, vomiting or diarrhea) not optimally managed per institutional guidelines	Withhold AK-01 until event returns to Grade 1 or baseline. The first time the event occurs, maintain the AK-01 dose level when dosing is resumed.  Each time the Grade 3 event recurs, withhold AK-01 until event returns to Grade 1 or baseline, then decrease AK-01 dosing frequency- when dosing is resumed. If the event recurs at 25 mg QD, the patient will be withdrawn.
Grade 4 (except alopecia, nausea, vomiting or diarrhea) not optimally managed per institutional guidelines	Patient will be withdrawn. Patient may not be rechallenged unless discussed with sponsor and approved by the SAC.
Hematologic Toxicity	
Platelets ≤Grade 1  ANC ≤Grade 1 on Day 1 and/or ANC ≤Grade 2 on Day 8 or 15	Continue at current dose level.

Platelets  $\geq$ Grade 2,  
ANC  $\geq$ Grade 2 on Day 1,  
ANC  $\geq$ Grade 3 on Day 8 or 15,  
and/or  
 $\geq$ Grade 3 platelets or ANC with  
spontaneous bleeding at any  
time

Withhold AK-01 until platelets  $\leq$ Grade 1 and ANC  
 $\leq$ Grade 1 (Day 1) or  $\leq$ Grade 2 (Day 8 or 15). Consider  
granulocyte colony stimulating factor (G-CSF) for low  
ANC. Decrease AK-01 dosing frequency when dosing is  
resumed.

Each time the Grade 3 event recurs, withhold AK-01  
until counts recover. Consider G-CSF for low ANC. If  

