### 5.2.2. Dose and Regimen

AK-01 will be administered twice daily, every day of a 21-day cycle. Patients will be dosed continuously: there will be no dosing holiday between cycles.

In Phase I, the dose of AK-01 will be between 25-75 mg BID per day (see [Table 3](#)). Patients in the first cohort of Phase I will receive 25 mg BID AK-01. Following a review of safety and other relevant data from this cohort, the SAC will decide on the dose for the subsequent cohort based on [Table 3](#). Following DLT or completion of Cycle 1, dosing for a given patient will be based on individual safety and tolerability.

For Phase II, the sponsor and SAC has established the dose of AK-01 as 25mg BID.

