#### 5.1.2. Phase II

Phase II will evaluate the preliminary efficacy of AK-01 in up to 4 cohorts; initially in patients with locally advanced or metastatic small-cell lung cancer (SCLC) and breast cancer (BC), and subsequently, at sponsor's discretion, in patients with TNBC, SCC-HN, and OT. Up to 30 patients may be enrolled in each cohort, giving an estimated total of 120 patients. Since AK-01 is an experimental treatment, patients will need to have failed standard of care therapies (i.e., platinum-

based therapy for SCLC; hormone therapy and a CDK4/6 inhibitor for BC; relapsed/resistant TNBC patients; standard therapy for HPV associated SCC-HN) before being enrolled in this trial.

All open cohorts in Phase II may begin enrollment concurrently and will be dosed at 25 mg BID. Dose increases will not be allowed in Phase II.

After Cycle 1, dosing of AK-01 may continue in 21-day cycles until disease progression if the patient is receiving benefit, and is experiencing no severe toxicity in the opinion of the investigator.

Dose modifications for toxicity for both phases are described in the Protocol, Section 3.3.2.

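### The mandatory hepatic withdrawal rule in Protocol Section 3.1.1 is not carried into Table 1, so Table 1 permits a restart that Section 3.1.1 forbids, and the rule's scope after Phase I Cycle 1 is unclear

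*Protocol*

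**What the plan says.** **The rule.** Protocol Section 3.1.1 defines a DLT as a Cycle 1 event judged possibly or probably related to AK-01 that meets one of several criteria. The hepatic criterion is AST or ALT at least 5 times ULN with bilirubin above 2 times ULN. With liver tumor involvement it is AST and ALT at least 7 times ULN, with the same bilirubin limit. The item ends: "In addition, any patient with this degree of hepatic effect will be withdrawn from the study".

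**The general table.** Section 3.3.2 applies to toxicity arising at any time in the study. It allows a pause: "IMP may be withheld for up to 21 days to allow sufficient time for recovery from toxicity". Table 1 has three blocks: QTcF prolongation, other non-hematologic toxicity and hematologic toxicity. For other non-hematologic toxicity at Grade 3, AK-01 is held until Grade 1 or baseline, and then: "The first time the event occurs, maintain the AK-01 dose level when dosing is resumed". At Grade 4 the patient is withdrawn, but with a route back: "Patient may not be rechallenged unless discussed with sponsor and approved by the SAC".

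**The pointers.** For Phase II, Section 3.2 reads "Dose increases will not be allowed in Phase II. Dose modifications for toxicity are described in" Section 3.3.2. SAP Section 5.1.2 agrees: "Dose modifications for toxicity for both phases are described in the Protocol, Section 3.3.2". Section 3.1.4 sends Phase I patients to the same place, and Section 5.2.2 adds: "Following DLT or completion of Cycle 1, dosing for a given patient will be based on individual safety and tolerability".

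**The concern.** The sponsor judged this liver pattern serious enough to require withdrawal, with no discretion. The table that sites will actually use to manage toxicity does not contain that stop. A site following Table 1 as written could restart AK-01, at an unchanged dose, in a patient whom Section 3.1.1 would have withdrawn.

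What is at stake is rechallenge after apparent recovery. It is not dosing through an active event, because Table 1 requires the event to resolve first and Section 3.3.2 limits the hold to 21 days.

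**Working it through.** No sample size, power or alpha figure is involved, so the check is a comparison of texts.

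**Step 1. Is the event covered elsewhere in Table 1?** No row mentions AST, ALT, bilirubin or the liver. The exceptions in the non-hematologic Grade 3 and Grade 4 rows are alopecia, nausea, vomiting and diarrhea. A hepatic event therefore falls in the generic rows. Table 1 shows no redaction, so the missing row is not a redaction effect.

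**Step 2. Apply both sections to the same event.** The trigger in 3.1.1 is in multiples of ULN, while Table 1 works by CTCAE grade. The grade cut-offs are not reproduced in the documents, so both branches are shown.

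| Event meeting the 3.1.1 hepatic thresholds | Section 3.1.1 | Table 1 |
|---|---|---|
| Graded 3, first time | Withdraw | Hold, then resume at the same dose after return to Grade 1 or baseline |
| Graded 4 | Withdraw | Withdraw, but rechallenge possible after sponsor discussion and SAC approval |

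The two disagree in both branches, more sharply at Grade 3. There, Table 1 does not ask even for the step from 25 mg BID to 25 mg QD at the first event. Recovery to baseline may also be recovery to a raised level: Section 4.1.1 admits patients with liver involvement at AST and ALT up to 5 times ULN, although bilirubin is capped at 1.5 times ULN.

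**Step 3. Which section governs when?**

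- *Phase I Cycle 1.* Both apply. Section 3.1.1 requires withdrawal for the hepatic event, then says that patients with a DLT may be discontinued and points to Section 3.3.2. No text ranks the two.
- *Later Phase I cycles.* The DLT definition has lapsed and the pointers lead to Section 3.3.2. Section 3.1.4 makes keeping or raising the dose conditional: "Following Cycle 1, if no DLT-equivalent toxicity is experienced". That calls an unchanged dose into question after such an event, but it does not require withdrawal.
- *Phase II.* Section 3.2 and SAP Section 5.1.2 lead only to Section 3.3.2. The words about any patient in 3.1.1 could be read as study-wide, or as confined to the definition that contains them.

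**Step 4. Does another section restore the stop?** Section 4.2.1 lists unacceptable toxicity as grounds for stopping treatment, with no liver threshold. It allows withdrawal but does not require it. By contrast, the serious cardiac event is carried across: Grade 4 QTcF prolongation is a DLT in 3.1.1 and leads to termination of treatment in Table 1.

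**Step 5. Size.** The documents give no rate for this event, and the potential adverse events visible in Sections 1.3 and 3.3.1 include no hepatic signal. Only time under Table 1 can be counted. Over 8 cycles of 21 days (8 × 21 = 168 days), a Phase I patient is outside the DLT window for 168 − 21 = 147 days, or 147/168 = 87.5%. A Phase II patient is outside it throughout. These figures assume that all 8 cycles are completed. They describe exposure to the rule, not risk.

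**The case against.** The strongest defense is that the difference may be intended. The sentence sits among rules for dose escalation, while Phase II is fixed at 25 mg BID, below the 50 mg and 75 mg levels at which Section 1.3 reports DLTs. If the rule is for Phase I Cycle 1 only, every later-cycle and Phase II site follows Table 1 in the same way. This stands, and it defeats one tempting inference: that sites would diverge whichever reading was meant. Divergence needs sites to read 3.1.1 differently, which the text allows but does not make inevitable.

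A second defense is that a specific, mandatory stop naturally overrides generic rows introduced as permitted modifications. That is a sensible way to resolve Phase I Cycle 1, but no text says so, and it does not settle Phase II.

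Third, there are safeguards:

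- Appendix 1 requires safety results acceptable to the investigator before dosing.
- A Grade 4 event already means withdrawal unless the SAC approves otherwise.
- The SAC meets at least quarterly.
- SAP Section 9.8.2 tabulates DLT-equivalent toxicities without limiting that table to Phase I.

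These narrow the hazard mainly to a first Grade 3 event that resolves within 21 days and is restarted. None requires withdrawal in that case.

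Fourth, Section 3.3.1 has redacted blocks that may contain hepatic guidance. If they hold a stopping rule, sites already have the instruction, and what remains is a drafting mismatch with Table 1.

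**Conclusion.** The point holds in limited form. Section 3.1.1 and Table 1 give different instructions for the same hepatic event in Phase I Cycle 1. For later cycles and Phase II the visible text does not settle whether the mandatory stop applies, so sites that read 3.1.1 differently could act differently.

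Two stronger readings are not supported. A reader might take the share of days under Table 1 as evidence of a substantial hazard. It is not: no event rate is given, no hepatic signal is visible, and many patients may stop before cycle 8. A reader might also conclude that the plan has no hepatic guidance for Phase II. The redactions in Section 3.3.1 rule out that claim.

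The MTD rule and the ORR test are not affected. This is a cheap improvement in patient-safety consistency, of low to moderate priority. It rests on Table 1 being complete as shown and on no redacted text stating which section prevails.

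**What to change.** Add a row to Table 1 for both phases and all cycles. When the 3.1.1 hepatic thresholds are met and the event is considered possibly or probably related to AK-01, AK-01 is permanently discontinued and follow-up continues. Exclude this event from the generic non-hematologic rows, cross-refer to the new row from Sections 3.1.1 and 4.2.1, and make it agree with any hepatic text in the redacted part of Section 3.3.1.

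Stopping the drug rather than leaving the study is a deliberate change from 3.1.1. Section 4.2.1 lists toxicity as a reason to stop treatment and does not name it among reasons to leave the study.

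If the sponsor meant the rule for Phase I Cycle 1 only, say so in 3.1.1 and state the hepatic action for later cycles and Phase II.

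No visit or test is added, because AST, ALT and bilirubin are already in the scheduled chemistry panel (Appendix 2). The cost is clinical: some patients who recover lose the chance to restart. The relatedness condition will not screen out every event caused by liver metastases or biliary obstruction. Section 6.5.3 lets an event count as possibly related when a causal link is improbable but cannot be excluded, and Section 8.2 treats unknown causality as related.

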#### 3.1.2. Maximum Tolerated Dose

The MTD is the dose immediately below the dose at which  $\geq 2/3$ ,  $\geq 2/6$ , or  $\geq 3/9$  patients in a cohort experience a DLT during the first 21 days of treatment (Cycle 1).

### 3.1.3. Dose Escalation Rules

[figure not shown]
The starting dose for the first cohort will be 25 mg BID AK-01, administered orally for 21 days. Each cohort will initially enroll up to 3 patients, and may be expanded up to 9 patients based on the dose escalation rules. At least 3 patients must complete Cycle 1 or experience a DLT before any dose escalation decision may be made. In the first cohort only, one patient will initially be dosed alone; if no DLT is experienced within 24 hours of the first dose, the remaining patients in the cohort may be dosed. Starting in cohort 2, patients may be dosed concurrently.

Dose escalation will be guided by the following rules (depicted graphically in [Figure 2](#)):

- If none of the 3 patients in a cohort experience a DLT during Cycle 1, the dose may be escalated for the subsequent cohort. If  $\geq 2$  patients out of 3 experience a DLT during Cycle 1, the MTD has been exceeded and no additional patients will be enrolled at that dose level. If 1 patient out of 3 experiences a DLT during Cycle 1, the cohort will be expanded with an additional 3 patients.
- If  $\geq 1$  DLT is observed in the additional 3 patients ( $\geq 2/6$ ), the MTD has been exceeded and no additional patients will be enrolled at that dose level. If no DLT is observed in the additional 3 patients ( $1/6$ ), the dose may be escalated for the subsequent cohort. Alternatively, if no DLT is observed in the additional 3 patients ( $1/6$ ) but further assessment of toxicity at the dose level is warranted, the sponsor (in conjunction with the investigator) may decide to enroll an additional 3 patients at that dose level.
  - If  $\geq 2$  DLT are observed in the additional 3 patients ( $\geq 3/9$ ), the MTD has been exceeded. If  $\leq 1$  DLT is observed in the additional 3 patients ( $\leq 2/9$ ), the dose may be escalated for the subsequent cohort.

A schematic for the dose escalation rules for any dose level in this study is presented in [Figure 2](#).

